Aim 5: We will offer enrollment to 20 adolescents living with HIV (ages 15 to 19 years old) accessing antiretroviral therapy at Mahatma Gandhi Hospital and KwaMashu Poly Clinic into two separate focus groups and who were enrolled in the randomized control trial in Aim 3 of this study to pilot testing the mobile health intervention. Informed consent and assent will be obtained as outlined below. We will review the importance of confidentiality within the focus group and that all information discussed during the focus group should not be discussed outside of the group. As in Aim 2, these adolescents will have had prior interactions with each other based on their adolescent support group attendance on clinic days and during interactions in the waiting room of the clinic, thus there is no increased risk of disclosure of HIV status based on participation in the focus group. We will obtain feedback on the intervention using the UTAUT acceptance model.

Aim 6: We will provide the pre- and post-intervention questionnaire about sexual and reproductive health to adolescents living with HIV (ages 15 to 19 years old) accessing antiretroviral therapy at Mahatma Gandhi Hospital and KwaMashu Poly Clinic who were enrolled in the randomized control trial in Aim 3 of this study pilot testing the mobile health intervention. We anticipate enrolling all future participants after approval of the amended protocol with an n of approximately 60. Informed consent and assent will be obtained as outlined below. The questionnaire will be delivered on paper after the last session, with research staff available to help answer any questions.

Aim 7: We will offer enrollment to up to 20 conveniently sampled adolescents living with HIV (ages 15 to 19 years old) accessing antiretroviral therapy at Mahatma Gandhi Hospital and KwaMashu Poly Clinic into two separate focus groups and who were enrolled in the randomized control trial in Aim 3 of this study to participate in a 60-minute semi-structured, in-depth interview. Informed consent and assent will be obtained as outlined below. We will review the importance of confidentiality and anonymity with the participants before beginning the interviews, and ensure that they can refuse to answer any questions and stop the interview at any point.

InTSHA: Interactive Transition Support for HIV-infected Adolescents Using Social Media - Detailed Protocol

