Aim 6: The same subjects enrolled in Aim 3 will be provided with a pre- and post- intervention questionnaire. During visit one, we will collect data on an additional 9 questions about consent, contraception, family planning, social pressures, and communication related to SRH. The second research visit will take place 6 months after randomization, after the intervention has been completed, to assess changes in beliefs and attitudes towards SRH over time.

Data to be collected and when the data is to be collected

InTSHA: Interactive Transition Support for HIV-infected Adolescents Using Social Media - Detailed Protocol

An additional 9 questions about attitudes and beliefs on SRH will be collected by adding to the existing pre and post questionnaire.

Aim 7: We will recruit participants from adolescents who participated in the clinical trial in Aim 3 from Mahatma Gandhi Hospital's and KwaMashu Poly Clinic's Pediatric and Adult HIV Clinics. Adolescent participants will be identified and referred by the hospital clinicians after clinic visits. We will conveniently sample up to 20 adolescents (based on saturation of major themes) who completed the intervention. We will attempt to enroll equal number of male and female participants of varying ages. Interviews will be conducted in isiZulu or English and last about 1 hour. **Measures:** The in-depth interviews will evaluate personal experiences with sexual and reproductive health as adolescents living with HIV based on the Theory of Planned Behavior and how our mobile health intervention affected attitudes and beliefs of sexual and reproductive health. We will aim for thematic saturation in each group.

Aims 8: We will recruit only patient previously enrolled in the InTSHA study. Participants will complete the same follow-up questionnaire that was completed at the end of the study. Participants will have a single blood draw to evaluate long term viral suppression.

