Aim 5 and 7: We will analyze the stigma- and sexuality-focused interventions using the plan, engage, execute, reflect and evaluate process.(55, 56) We will then conduct the focus group based on the UTAUT model of technology acceptance to reflect on usefulness and acceptability of the

InTSHA: Interactive Transition Support for HIV-infected Adolescents Using Social Media - Detailed Protocol

intervention.(57) The focus group discussions will evaluate the usability, challenges, and expectations of the intervention. The discussions will be recorded, transcribed, and translated into English. Transcriptions will be uploaded, organized, and coded using Dedoose software (version 7.0.23, LA, California).(52) I will use an iterative process as described in Aim 2 after each focus group session with adolescents to evaluate feedback for each version of the stigma- and sexuality-based interventions based on coded themes identified during focus group feedback sessions. The content will be revised based on focus group feedback prior to demonstration with the second focus group. The final intervention content will be based on the iterative process from both focus groups, as well as input from our collaborative research team. We will train the research team using an intervention manual for content to ensure consistency of the intervention. Only one team will monitor and facilitate the sessions. Aim 6: We will summarize the sexual and reproductive health pre- and post- questionnaire data using standard summary statistics (e.g. counts/percentages; median and interquartile range of continuous measures). The questionnaire tests comfort with SRH topics in a uniformly negative (strongly disagree) to positive (strongly agree) 4 point Likert scale. We will estimate the difference in aggregate and question-specific score improvement between the intervention group and the control group in aggregate score on the questionnaire.

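### Aim 6 compares the arms on questionnaire score improvement without adjusting for the visit-one score, which gives up precision that the collected data would supply at almost no cost

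*Combined protocol and SAP*

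**What the plan says.** Section VII, Statistical methods, Aim 6 begins with description: "We will summarize the sexual and reproductive health pre- and post- questionnaire data using standard summary statistics". It then gives the aim's only between-arm analysis: "We will estimate the difference in aggregate and question-specific score improvement between the intervention group and the control group". Responses lie on a "uniformly negative (strongly disagree) to positive (strongly agree) 4 point Likert scale". No model, covariate, test, effect size, SD or power is given for this aim.

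The baseline is collected. Section VI, Aim 6 states: "The same subjects enrolled in Aim 3 will be provided with a pre- and post- intervention questionnaire", and then "During visit one, we will collect data on an additional 9 questions about consent, contraception, family planning, social pressures, and communication related to SRH". On the follow-up it says: "The second research visit will take place 6 months after randomization, after the intervention has been completed". Section IV, Aim 6 gives the size: "We anticipate enrolling all future participants after approval of the amended protocol with an n of approximately 60". Under Aim 3 the same section sets 1:1 randomization.

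The plan does not define improvement. Aim 6 in Section II speaks of patterns of change, and Section VI of changes in beliefs and attitudes, so post minus pre is the natural reading. The only regression anywhere in the plan is an optional logistic model under Aims 3 and 8 for retention and viral suppression.

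**The concern.** A difference in improvement uses the baseline by subtraction, which fixes the coefficient of the visit-one score at 1. Regression instead estimates that coefficient from the data. With equal SDs at the two visits, the best value is the pre-post correlation, which is below 1. Subtraction therefore over-corrects and adds noise. When the correlation is below 0.5, the improvement score is noisier than the post score with the baseline ignored.

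What is at stake is the width of the interval around the only randomized estimate for Aim 6. With about 60 participants the interval is already wide, and a pilot cannot easily add more. The plan gives no reason for preferring the improvement score, and the data for the tighter estimate are already being collected.

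**Working it through.** **The plan's own figures.** Aim 6 has none to reproduce. The only power statement in the plan, for acceptability under Aim 3, does reproduce: rejecting at 34 or more of 40 gives exact one-sided alpha 0.0238 and power 0.9005, against the stated 90%. It has no bearing on this point.

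**Inputs**
- About 60 participants (Section IV, Aim 6), randomized 1:1 (Section IV, Aim 3). Taken as 30 per arm.
- Assumed, because the plan is silent: equal SDs at the two visits (set to 1), independent participants, and a pre-post correlation ρ shown over a range.

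**Formulas**
- Variance of the between-arm difference in improvement: (2/30) × 2(1−ρ).
- Variance of the baseline-adjusted difference, large sample: (2/30) × (1−ρ²).
- Ratio, adjusted to improvement: (1+ρ)/2.
- Cost of estimating the slope with 60 participants: multiply the adjusted variance by about 1 + 1/56 = 1.0179.

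| Assumed ρ | SE, improvement | SE, adjusted (large sample) | (1+ρ)/2 | × 1.0179 | Variance cut |
|---|---|---|---|---|---|
| 0.3 | 0.306 | 0.246 | 0.65 | 0.662 | 34% |
| 0.5 | 0.258 | 0.224 | 0.75 | 0.763 | 24% |
| 0.7 | 0.200 | 0.184 | 0.85 | 0.865 | 13–14% |
| 0.9 | 0.115 | 0.113 | 0.95 | 0.967 | 3% |
| 0.97 | – | – | 0.985 | 1.003 | none (slight loss) |

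The break-even point is (1+ρ)/2 = 56/57, that is ρ = 0.965. For comparison, the post score alone has SE √(2/30) = 0.258. Improvement matches it at ρ = 0.5 and is worse below that.

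**What this means at ρ = 0.5.** Matching the adjusted precision with improvement scores would take 60/0.763, or about 79 participants. For an assumed difference of 0.5 SD at a two-sided 5% level (noncentral t), power is 47.8% for improvement and 59.4% adjusted, or 58.7% once the slope cost is included. The 95% half-width goes from 0.52 to 0.45 SD. These power figures are illustrative, since the plan sets no test for this aim.

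**Chance imbalance.** The baseline difference between arms has SD √(2/30) = 0.258. Given an imbalance D, the expected improvement contrast moves by −(1−ρ)D. At ρ = 0.5 a one-SD imbalance moves it by 0.5 × 0.258 = 0.129 SD, in favour of the arm that started lower. This is not an additional loss: 2(1−ρ) = (1−ρ²) + (1−ρ)², so the imbalance term is exactly the variance gap in the table.

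**Check on the actual kind of scale.** A simulated sum of nine 4-point items (60 participants, 6,000 runs) gave these empirical SEs in points:

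| Observed ρ | Improvement | Adjusted | Variance cut |
|---|---|---|---|
| 0.35 | 1.918 | 1.581 | 1 − (1.581/1.918)² = 32% |
| 0.52 | 1.615 | 1.438 | 1 − (1.438/1.615)² = 21% |
| 0.70 | 1.277 | 1.189 | 1 − (1.189/1.277)² = 13% |

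Both estimators averaged close to zero when there was no effect. The improvement estimate correlated −0.58, −0.47 and −0.39 with the baseline imbalance, and the adjusted estimate about 0.

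**The case against.** **The sentence names a quantity, not a model.** Regressing improvement on arm and baseline gives the same arm coefficient as regressing the post score on arm and baseline, so the text does not forbid the better analysis. The sentence also repeats the aggregate score at its end, so it may not reflect a deliberate choice. This is fair as to intent. Followed as written, however, the sentence produces an unadjusted contrast, and nothing elsewhere supplies the covariate.

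**Stronger readings that the documents do not support:**
- *That the comparison is biased.* Under randomization both arms regress to the mean alike, and the improvement contrast is unbiased on average.
- *That improvement scores are always worse.* At this sample size the advantage of adjusting vanishes above a correlation of about 0.965 and is only about 3% at 0.9.
- *That the single questions must have low test-retest correlation.* This is plausible for 4-point items, but the plan gives no figure.
- *That the plan's conclusion about mHealth efficacy rests on this estimate.* Section II, Aim 7 draws that conclusion from the Aim 7 interviews together with Aim 6.

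**Participants may not be independent.** Section VI, Aim 3 enrols in groups of 5 to 10. Suppose an intraclass correlation of 0.1 in the intervention arm only, with groups of 7.5. That adds 0.1 × 6.5 = 0.65 to that arm's variance, or 0.325 averaged over the arms. At ρ = 0.5 the large-sample ratio becomes (0.75 + 0.325)/(1 + 0.325) = 0.811, a cut of 19% instead of 25%. The gain shrinks but remains.

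**The priority is low.** This stands. Section VII, Aim 3 puts the primary focus on acceptability and feasibility and ties the step to a larger trial to retention and viral suppression, not to the SRH questionnaire.

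**Conclusion.** The point holds as a matter of precision. The Aim 6 between-arm comparison, read naturally, is an unadjusted difference in improvement. Adjusting for the visit-one score would cut its variance by about a third at a correlation of 0.3, about a quarter at 0.5 and about a seventh at 0.7, with little or nothing gained from 0.9 upward. These sizes rest on equal SDs, 30 per arm, independent participants and an assumed correlation, because the plan gives none. Aim 6 is an unpowered secondary aim of a pilot, so this is an optional improvement.

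**What to change.** In Section VII, Statistical methods, Aim 6, replace the comparison sentence with wording such as: *The between-arm difference in the aggregate post-intervention SRH score will be estimated by linear regression on arm and the visit-one aggregate score, with a 95% confidence interval. Each question will be compared between arms with adjustment for its own visit-one response. Mean improvement by arm will be reported descriptively.* If the team prefers to keep improvement as the outcome, adding the visit-one score as a covariate gives the same arm estimate. Linear regression is a simplification for single 4-point items. An ordinal model with the same covariate would also meet the point.

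Before fixing the time point, reconcile Section IV, Aim 6, which has the questionnaire given on paper once the last session is over, with Section VI, Aim 6, which places it at the 6-month visit. No sessions are described for the standard-of-care arm, so the text should state one time point that applies to both arms.

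The cost is one or two sentences, one covariate and one degree of freedom. No new data, visits or participants are needed.

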AIM 1: After obtaining institutional and all relevant IRB approvals, we will offer enrollment to adolescents living with HIV (ages 15 to 19 years) accessing antiretroviral therapy at Mahatma Gandhi Hospital who remain in pediatric care, those that have transitioned to adult care, and those who were lost to care during the transition process as determined by prior research study. Participants will be referred to study staff by HIV clinicians. We will also offer enrollment to caregivers of adolescents living with HIV after the adolescent as given assent or consent to participate. In addition, we will offer enrollment to healthcare providers caring for HIV-infected adolescents prior to or after transition to adult care.

Participants will participate in an in-depth interviews focusing on topics:

Optimal platforms
WhatsApp, Facebook, Snapchat, MIXIT to determine acceptability, usability, flexibility, data requirements
Social media issues
Social media use, privacy of cellular phone and online data, cyber bullying
Modifiable factors from SMART model
Knowledge, self-efficacy, beliefs, maturity, goals/motivation, relationships with clinical staff, peer and social support, experience with HIV disclosure and stigma

AIM 2: We will offer enrollment to 20 HIV-infected adolescents (ages 15 to 19 years) accessing antiretroviral therapy at Mahatma Gandhi Hospital into two separate focus groups. In addition, we offer enrollment two separate focus groups of healthcare providers (10) and a focus group with caregivers (10). Informed consent and assent will be obtained as below.

We will review the importance of confidentiality within the focus group and that information discussed in the focus group should not be discussed outside of the focus group. These adolescents will have had prior interactions with each other based on their adolescent support group attendance on each clinic day and on interactions in the waiting room of the clinic. For this reason, there is no increased risk of disclosure of HIV status based on participation in the focus group.

In each focus group we will demonstrate the behavioral intervention using social media and encourage active participation in the use of social media intervention. We will then use obtain feedback on the intervention based on the Unified Theory of Acceptance and Use of Technology (UTAUT) technology acceptance model.

InTSHA: Interactive Transition Support for HIV-infected Adolescents Using Social Media - Detailed Protocol

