Aim 5: The intervention will be a social media-based interactive motivational interviewing intervention for youth living with HIV during healthcare transition. Content will incorporate findings from existing data from in-depth interviews in Aim 1 & 4, intervention mapping and interactive strategies using principals of motivational interviewing, in addition to an informational component. The informational component will address misconceptions about HIV and healthcare transition, aiming to reduce fears about transition through education, graphics, and videos. To promote attitude and behavior change, motivational interviewing will be used including open-ended questions, affirmations, reflective listening, and exploration of reasons for stigma. Participants enrolled in the randomized control trial in Aim 3 of this study will pilot test the stigma intervention module for InTSHA. We will use an iterative process with 2 separate focus groups of 8 - 10 adolescents each who have used the stigma intervention module for InTSHA. Focus groups will be conducted separately for English and Zulu and will last approximately 90 minutes. The focus groups will be conducted based on the UTAUT model of technology acceptance to reflect on usefulness and acceptability of the intervention.(37) The focus group discussions will evaluate the usability, challenges, and expectations of the intervention. The discussions will be recorded, transcribed, and translated into English. Transcriptions will be uploaded, organized, and coded using Dedoose software (version 7.0.23, LA, California).(38) We will identify coded themes during the first focus group session and use an iterative process to evaluate feedback for each version of the intervention. The intervention will subsequently be revised based on focus group feedback prior to demonstration with the next round of focus group participants. The final intervention will be based on the iterative process from both focus groups as well as input from our collaborative research team. To ensure fidelity of the intervention, we will use an intervention manual for content with training of the research team. Only one team will monitor and facilitate the sessions.

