Safeguard: The data from interviews and medical record review will be anonymous and identifiable information will not be recorded. All information will be stored on encrypted password-protected computers and loaded into a secure REDCap and Dedoose databases. Interviews will take place in a private setting. Participant names will not be recorded and personal identifiers will be limited to date of birth. Participants will be identified only by a unique study ID number. While the data is being collected, the list linking study ID numbers to patient file numbers (medical record numbers) will exist. This is necessary for cross-referencing the different data sources. Once all data has been collected, the list that links study ID numbers to medical record numbers will be permanently deleted. All steps in this de-identification process will occur on the password-protected, encrypted, study computer. Participants will be shown how to password protect their mobile phone. Only adolescents randomized to the intervention and study staff will have access to the social media site. Patient names or identifying information will not be used in online communications.

Risk: Loss of privacy including disclosure of HIV status during focus group discussions.

InTSHA: Interactive Transition Support for HIV-infected Adolescents Using Social Media - Detailed Protocol

Safeguard: Adolescents will be enrolled from Mahatma Gandhi Clinic and KwaMashu Poly Clinic. Current procedures at the clinic include attendance in an adolescent support group on clinic days. Since adolescents will be recruited from this site, they will already have interacted with each other during these group meetings as well as in the waiting room of the clinic. This will minimize accidental disclosure of HIV status among focus group members. In addition, we will review the importance of confidentiality within the focus group and that information discussed in the focus group should not be discussed outside of the focus group.

Risk: Loss of privacy including accidental disclosure of HIV status using social media.

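### The Aim 5 statement that focus groups carry no added risk of HIV-status disclosure is unsupported for members who attend different clinics

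*Combined protocol and SAP*

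**What the plan says.** Section IV (Subject Enrollment), Aim 2, recruits 20 adolescents "accessing antiretroviral therapy at Mahatma Gandhi Hospital into two separate focus groups". It argues that they know each other from the support group and the waiting room, and concludes that taking part adds no risk of disclosure.

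Section IV, Aim 5, refers back to Aim 2 and reuses the argument. It recruits 20 adolescents "accessing antiretroviral therapy at Mahatma Gandhi Hospital and KwaMashu Poly Clinic into two separate focus groups". The premise is that "these adolescents will have had prior interactions with each other based on their adolescent support group attendance on clinic days", and the conclusion is "thus there is no increased risk of disclosure of HIV status based on participation in the focus group".

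Section VI (Study Procedures), Aim 5, plans "2 separate focus groups of 8 - 10 adolescents each who have used the stigma intervention module for InTSHA". On how they are run it says: "Focus groups will be conducted separately for English and Zulu". It does not mention clinic.

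Section VIII (Risks and Discomforts), in the safeguard for focus-group discussions, names Mahatma Gandhi and KwaMashu Poly Clinic. It then treats recruitment as coming from one site and says "they will already have interacted with each other during these group meetings". Its conclusion is milder than that of Section IV: prior contact is said to minimize accidental disclosure. A confidentiality reminder is added.

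**The concern.** The safety statement for Aim 5 is absolute and has a single stated support, prior contact between members. That support is local to a clinic. Two patients of one clinic may well have shared its support group and waiting room. For a patient of Mahatma Gandhi and a patient of KwaMashu, the documents give no reason to think so. If the two sit in one focus group, attending can itself tell each that the other has HIV, because the group is for adolescents living with HIV who have used a stigma module.

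Loss of privacy involving HIV status appears in each of the first three risks in Section VIII. Eligible adolescents are 15 to 19 years old, so some may be minors whose caregivers also consent. Section V requires the consent discussion to cover risks and the protections against them. An unsupported assurance in the protocol can carry over into that discussion.

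**Working it through.** The plan gives no figure on this point, so the check is mainly a comparison of the text.

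**Step 1. Compare the passages.**

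| Place | Clinics | How groups are formed | Stated basis | Conclusion |
|---|---|---|---|---|
| Section IV, Aim 2 | One | Two adolescent groups | Prior contact at the clinic | No added risk |
| Section IV, Aim 5 | Two | Two groups, no clinic rule | Same, by reference to Aim 2 | No added risk |
| Section VI, Aim 5 | Not mentioned | By language, 8 to 10 each | None given | None given |
| Section VIII | Two named, then one site | Not stated | Prior contact at the clinic | Risk minimized |

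**Step 2. Test the inference.** In Aim 2 all adolescents come from one hospital, so the premise of prior contact can apply to every pair of members. In Aim 5 it can apply only to pairs from the same clinic. The conclusion would carry over if groups were kept within a clinic, or if patients of the two clinics shared a support group or waiting room. The documents state neither. Reading the single site in Section VIII as each site separately still covers same-clinic pairs only.

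**Step 3. How likely are single-clinic groups if clinic is ignored? (Illustration.)** Inputs: group size m = 8 or 10, from Section VI, Aim 5, and an assumed share s of participants from the larger clinic, which the documents do not give. Members are treated as drawn independently and without regard to clinic or to any link between clinic and language.

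P(one group is single-clinic) = s^m + (1 − s)^m

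P(both groups are single-clinic) = [s^m + (1 − s)^m]²

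For example, with s = 0.8 and m = 8: 0.8^8 + 0.2^8 = 0.168, and 0.168² = 0.028.

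| Assumed split | One group, m = 8 | One group, m = 10 | Both groups, m = 8 | Both groups, m = 10 |
|---|---|---|---|---|
| 50/50 | 0.8% | 0.2% | 0.01% | under 0.01% |
| 70/30 | 5.8% | 2.8% | 0.3% | 0.1% |
| 80/20 | 16.8% | 10.7% | 2.8% | 1.2% |
| 90/10 | 43.0% | 34.9% | 18.5% | 12.2% |

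**Step 4. How many pairs would lack the stated safeguard? (Illustration.)** A group of 10 has 10 × 9 / 2 = 45 pairs. At an assumed 5/5 clinic split, 5 × 5 = 25 pairs (56%) are cross-clinic. At 8/2 it is 8 × 2 = 16 pairs (36%). In a single-clinic group it is 0. These counts show how far the safeguard reaches. They do not measure the risk of disclosure.

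**The case against.** The strongest reply is that mixing is inferred. The protocol does not say that a group will contain patients of both clinics, and a within-clinic arrangement would fit the Section IV text. This stands, and it limits the point to something the plan leaves open. It does not rescue the statement, because an assurance of no added risk needs the arrangement that would make it true, and none is given.

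There is also mitigation:

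- **Earlier online contact.** Aim 5 members are Aim 3 trial participants who have used the module. The intervention runs in a closed, invitation-only group, and Section VI anticipates enrolling participants in groups of 5 to 10. Some members may therefore have met online. This helps in part, but Section VIII says names and identifying details are not used online, and the protocol does not rely on such contact for its conclusion.
- **Mutual disclosure.** Every adolescent must be perinatally infected and aware of it, so disclosure inside the room is mutual. That may soften the harm, but it is still disclosure to someone new.
- **Confidentiality reminder.** It does not depend on site, but it addresses repetition outside the room and not recognition within it.

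A reader might also infer that patients of the two clinics have never met, so that the statement is false. The documents are silent on contact between the clinics and do not support that. Nor do they show that families are left uninformed: the consent forms are not in the file reviewed and may already mention the other clinic.

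**Conclusion.** The point holds in a limited form. The Aim 5 statement in Section IV is unsupported for any members who come from different clinics, because an argument that fits the single-site Aim 2 was carried over to a two-clinic design. Section VIII contains the same slip from two clinics to one site, with a weaker conclusion.

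The size is modest. It concerns about 20 adolescents in a qualitative aim and does not touch randomization, the primary outcomes or the analysis. How many members are affected cannot be derived from the documents. If clinic is ignored when groups are formed, at least one mixed group is the likely result at every split examined: the chance that both groups are single-clinic is at most 2.8% up to 80/20 and at most 18.5% at 90/10. That rests on assumed splits, independent draws and no link between language and clinic. It does not show that the groups will be mixed, and the text does not support saying that Aim 5 mixes the clinics by design.

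It is still worth correcting, because it is an absolute reassurance about disclosure of HIV status in a group that may include minors.

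**What to change.** Reconcile Section IV (Aim 5), Section VI (Aim 5) and Section VIII:

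1. Withdraw the statement of no added disclosure risk for Aim 5.
2. In Section VIII, limit the prior-contact safeguard to members of the same clinic and correct the single-site wording.
3. If the forms do not already say so, tell adolescents and caregivers in the assent and consent discussion that patients of the other clinic may attend, so that they can decline.

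This costs a few sentences and possibly a few more refusals. It leaves the language-based groups as they are.

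Alternatively, if groups are meant to be formed within a clinic, say so in Sections IV and VI. That is a trade-off: keeping the language split as well could mean 2 clinics × 2 languages = 4 groups of about 20 / 4 = 5 adolescents, below the planned 8 to 10. Giving up the language split would mean running mixed-language sessions. The wording change does not force that choice.
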